1.4 Who Would Benefit from this Treatment?

As noted above, there are several quite good but not perfect treatments for organ confined prostate cancer that have significant follow-up and published experience as well as an option for watchful waiting. Still, there are populations that might find the invasiveness of surgery and brachytherapy implants less ideal and the inconvenience of IMRT and 3-D conformal therapy impractical. General anesthesia is inappropriate for some patients due to significant co-morbid conditions. We believe a very abbreviated, non-invasive, outpatient treatment would be considered a favorable option in particular to the underserved populations of men living in more remote areas including farmers, ranchers, and those in rural communities. Furthermore, if the concept of prostate cancer having a very low alpha to beta ratio discussed previously is confirmed, this treatment using SBRT may in fact be a better option for some men with prostate cancer.

2.0 OBJECTIVES

- 2.1 In phase I, the primary objective is to escalate the dose of stereotactic radiotherapy to a tumorcidal dose without exceeding the maximum tolerated dose in patients with organ confined prostate cancer.
- 2.2 In phase I, a secondary objective is to determine the dose-limiting toxicity (if the maximum tolerated dose is reached).
- 2.3 In phase II, the primary objective is to determine the late severe grade 3-5 GU and GI toxicity from 270-540 days (i.e., 9-18 months) from the start of the protocol treatment. It is graded based on CTCAE v3.0.
- 2.4 In phase II, secondary objectives will be to determine the 2 year biochemical (PSA) control (freedom from PSA failure), disease free and overall survival, local control, freedom from distant metastases, and the incidence of high grade adverse events of any type from the therapy in the treated patients in order to determine if the therapy is promising enough for further clinical investigation.

3.0 PATIENT SELECTION

- 3.1 All patients must be willing and capable to provide informed consent to participate in the protocol.
- 3.2 Eligible patients must have appropriate staging studies identifying them as AJCC stage T1 (a, b, or c) or T2 (a and b only) adenocarcinoma of the prostate gland. The patient should not have direct evidence of regional or distant metastases after appropriate staging studies. Histologic confirmation of cancer will be required by biopsy.
- 3.3 The patient's Zubrod performance status must be 0-2
- 3.4 The Gleason score should be less than or equal to 7
- 3.5 The serum PSA should be less than or equal to 20 ng/ml prior to starting hormonal therapy (if given) for patients with Gleason score 2-6. For patients with Gleason score of 7, PSA should be less than or equal to 15 ng/ml prior to starting hormonal therapy (if given). As such, the risk of pelvic lymph node involvement according to the Roach formula would be under 20%.
- 3.6 Eligible patients should not have had previous pelvic radiotherapy or have had chemotherapy or surgery for prostate cancer. Hormonal therapy given for up to 9 months prior to SBRT is allowed as a neoadjuvant therapy or to downsize the prostate gland.
- 3.7 There must be no plans for the patient to receive other concomitant or post treatment adjuvant antineoplastic therapy while on this protocol including surgery, cryotherapy, conventionally fractionated radiotherapy, hormonal therapy, or chemotherapy given as part of the treatment of prostate cancer.
- 3.8 Patients should not have undergone previous transurethral resection of the prostate (TURP) or cryotherapy to the prostate.

- 3.9 Patients must be past their 18th birthday at time of registration.
- 3.10 Patients with history of inflammatory colitis (including Crohn's Disease and Ulcerative colitis) are not eligible.
- 3.11 Patients may have used prior hormonal therapy, but it should be limited to no more than 9 months or therapy prior to enrollment.
- 3.12 Patients should not have significant urinary obstructive symptoms; AUA score must be ≤ 15 (alpha blockers allowed).
- 3.13 The ultrasound or CT based volume estimation of the patient's prostate gland should not be greater than 60 grams.
- 3.14 Patients should not have a history of significant psychiatric illness.
- 3.15 Men of reproductive potential may not participate unless they agreed that they or their partner use an effective contraceptive method such as condom/diaphragm and spermacidal foam, intrauterine device (IUD), or prescription birth control pills.
- 3.16 Prior invasive malignancy (except non-melanomatous skin cancer) unless disease free for a minimum of 3 years (e.g., carcinoma *in situ* of the breast, oral cavity, or cervix are all permissible).
- 3.17 Severe, active co-morbidity, defined as follows:
 - 3.17.1 Unstable angina and/or congestive heart failure requiring hospitalization within the last 6 months.
 - 3.17.2 Transmural myocardial infarction within the last 6 months.
 - 3.17.3 Acute bacterial or fungal infection requiring intravenous antibiotics at the time of registration.
 - 3.17.4 Chronic Obstructive Pulmonary Disease exacerbation or other respiratory illness requiring hospitalization or precluding study therapy within 30 days before registration.
 - 3.17.5 Hepatic insufficiency resulting in clinical jaundice and/or coagulation defects; note, however, that laboratory tests for liver function and coagulation parameters are not required for entry into this protocol.
 - 3.17.6 Acquired Immune Deficiency Syndrome (AIDS) based upon current CDC definition; note, however, that HIV testing is not required for entry into this protocol. The need to exclude patients with AIDS from this protocol is necessary because the treatments involved in this protocol may be significantly immunosuppressive. Protocol-specific requirements may also exclude immunocompromised patients.
 - 3.17.7 History of treatment with potent immunosuppressive drugs for such conditions as post organ transplant, severe rheumatoid arthritis, etc. within the past 6 months.

4.0 PRETREATMENT EVALUATIONS/MANAGEMENT

Note: This section lists baseline evaluations needed before the initiation of protocol treatment that do not affect eligibility.

- 4.1 Required Evaluations/Management

- 4.1.1 History and physical examination to include digital rectal examination of the prostate, determination of AUA score, and completion of EPIC prostate quality of life questionnaire.
- 4.1.2 Zubrod performance status (Appendix II).
- 4.1.3 Lymph node evaluation performed within 90 days prior to registration by either CT or MRI (lymph node dissection is acceptable but not required).
- 4.1.4 Prostate Specific Antigen (PSA) prior to treatment (prior to hormonal therapy, if given).
- 4.1.5 See Section 11.1; note that failure to perform one or more of these tests may result in assessment of a protocol violation.

4.2 Highly Recommended Evaluations/Management

Cystoscopy, if advised by the urologist, may be performed to check for urethral damage including strictures, bladder pathology, or a large median prostate lobe. Anosocopic exam with initial and follow up exams.

5.0 REGISTRATION PROCEDURES

5.1.1 Preregistration Requirements for diagnostic pathology review

There are no requirements for central review of pathology used for initial diagnosis.

5.1.2 Pre-Registration Requirements for SBRT Treatment Approach

In order to utilize SBRT in this protocol, the institution must have met technology requirements and have provided a description of techniques, methods, training, and experience showing competency to the study PIs.

5.2 Registration

5.2.1 Fax Registration

Prior to registration, participating investigators and institutions should review the eligibility checklist and confirm eligibility. Patients can be registered only after eligibility criteria are met. To register a patient, the site should fax the Enrollment Form to the Project Manager ([contact]). A unique, participant ID number will then be assigned.

5.3 Accreditation

5.3.1 Institutional Processes

Prior to treating patients on protocol, the institution's specific methods for immobilization (e.g., frame vs. frameless), targeting, dose construction, daily verification of accuracy, ongoing assessment of accuracy and Quality Assurance policies must be described to and approved by the study PI and other approved institutional PIs. The primary purpose of accreditation will be to insure that dose is delivered to the targets and avoiding normal tissues according to protocol criteria. This accreditation may be assessed by written documentation, conference calls, or direct observation via site visits. Additional data may be required of institutions to verify that techniques are performing as intended.

6.0 RADIATION THERAPY

6.1 Dose Specifications

6.1.1 Stereotactic Targeting and Treatment

The term "stereotactic" for the purposes of this protocol implies the targeting, planning, and directing of therapy using beams of radiation along any trajectory in 3-D space guided by one or several fiducials of known 3-D coordinates. This differs from conventional radiation therapy in which therapy is directed toward skin marks or bony landmarks and assumed to correlate to the actual tumor target based on a historical simulation. It should be understood that Stereotactic Body

Radiation Therapy (SBRT) has become a treatment that is well beyond just stereotactic targeting. Indeed SBRT is mostly about ablative range dose per fraction, accounting properly for errors including motion, careful construction of dosimetry that compacts high dose into the tumor and not normal tissues, and extra careful treatment conduct. This protocol will require treatments to be conducted with the use of a fixed 3-D coordinate system defined by fiducials. The coordinate system defined by the fiducials should be directly related to the radiation producing device (e.g., couch and gantry) in a reproducible and secure fashion. Capability should exist to define the position of targets within the patient according to this same 3-D coordinate system. As such, the patient is set up for each treatment with the intention of directing the radiation toward an isocenter or target according to the known 3-D coordinates as determined in the process of treatment planning. The nature of the fiducials themselves may include radio-opaque markers or rods placed at known locations in a frame or fixed structure adjacent to the patient as well as use of the tumor itself as a fiducial (e.g. acquiring tomographic views of the tumor simultaneously with the treatment). Metallic "seeds" or markers placed within the tumor will be allowed so long as they are not prone to migration movement.

6.1.2 Dose Fractionation

Patients will receive 5 fractions of radiation. A minimum of 36 hours and a maximum of 8 days should separate each treatment. No more than 3 fractions will be delivered per week (7 consecutive days). Total dose will depend on the phase of the study (see schema).

6.1.3 Premedications

Unless contraindicated, it is recommended that all patients receive corticosteroid premedication (e.g. Decadron 4 mg p.o. in a single dose, or equivalent) 15-60 minutes prior to each of the five treatments for the intended purpose of modulating immediate acute inflammatory effects. It is strongly recommended that all patients be treated prophylactically with drugs intended to avoid urinary retention associated with SBRT. This class of drugs include alpha blockers (e.g., tamsulosin aka Flomax, doxazosin aka Cardura, terazosin aka Hytrin, etc) and 5-alpha reductase inhibitors (e.g., finasteride aka Proscar, dutasteride aka Avodart, etc), or drugs with similar intended effect. It is recommended to start the therapy at least one day prior to the first SBRT treatment and continue for 3 months post finishing all SBRT therapy. The drugs should be taken at standard doses for obstructive indications, and contraindications to these drugs should be respected. Analgesic premedication, such as Tylenol 650 mg 30 minutes prior to therapy and as needed every 6 hours, to avoid general discomfort during long treatment durations also is recommended when appropriate.

6.1.4 Supportive medicines

Consider Tamsulosin (e.g., Flomax) during treatment period to reduce urinary symptoms. Consider using 5-alpha reductase inhibitor like Finasteride (e.g. Proscar) to relieve potential obstructive issues. For both drugs, standard doses will be utilized as needed unless contraindicated. Also consider 1 tablespoon of Milk of Magnesia, taken the night before simulation/treatment (*Note: Inform patient that this will cause diarrhea*). Fleet's enema should be taken 2 hrs. before simulation/treatment. An antibiotic (Bactrim or similar) may be prescribed to alleviate UTI if necessary. This should be taken at standard doses as needed.

6.2 Technical Factors

6.2.1 Physical Factors

Only photon (x-ray) beams produced by linear accelerators, betatrons, or microtron accelerators with photon energies 6-21 MV will be allowed. Cobalt-60 and charged particle beams (including electrons, protons, and heavier ions) are not allowed.

6.2.1 *Dose Verification at Treatment*

Personal dosimeter measurements (e.g. diode, TLD, etc.) may be obtained for surface dose verification for accessible beams as per institutional preference. This information is not required by the protocol.

6.3 *Localization, Simulation, and Immobilization*

6.3.1 *Patient Positioning*

Patients will be positioned supine in a stable position capable of allowing accurate reproducibility of the target position from treatment to treatment. Positions uncomfortable for the patient should be avoided so as to prevent uncontrolled movement during treatments. A variety of immobilization systems may be utilized including stereotactic frames that surround the patient on three sides and large rigid pillows (conforming to patients external contours) with reference to the stereotactic coordinate system (see Section 6.1). All positioning systems must be validated and accredited by the Study Committee (Principal Investigator and Institutional PIs) prior to enrolling or treating patients on this trial. Patient immobilization must be reliable enough to insure that the Gross Tumor Volume (GTV) does not deviate beyond the confines of the Planning Treatment Volume (PTV) as defined in Section 6.4 with any significant probability (i.e., < 5%).

6.3.2 *Inhibition of Effects of Internal Organ Motion*

Special considerations must be made to account for the effect of internal organ motion (i.e., breathing, etc.) on target positioning and reproducibility. In some cases, the intrafractional tumor motion is small and no special maneuvers are required to achieve motion limits as defined in section 6.4 (this may be true for many cases of prostate cancer). Treating in the prone position will accentuate internal organ motion problems related to breathing and should be avoided unless special measures are taken to account for this motion. When accounting for intrafractional motion, acceptable maneuvers including reliable abdominal compression, accelerator beam gating with the respiratory cycle, and active breath-holding techniques. Internal organ inhibition maneuvers must be reliable enough to insure that the Gross Tumor Volume (GTV) does not deviate beyond the confines of the Planning Treatment Volume (PTV) as defined in Section 6.4 with any significant probability (i.e., < 5%). Assessment of this motion will be left to the institution and may include identifying the position of radio-opaque seeds implanted into the prostate prior to each treatment. This type of interfractional motion analysis with correction is only required by protocol just prior to each separate treatment. Intrafraction assessment during the course of each treatment (dynamic and adaptive maneuvers) is allowed and encouraged especially if treatment times are long.

6.3.3 *Localization and treatment maneuvers*

A more direct method of localization of the prostate gland than conventional treatment (i.e., one that uses skin and boney landmarks solely as a surrogate to the prostate position) must be used in this protocol. Acceptable methods would include daily ultrasound or placing a radio-opaque seed or marker that can be visualized and triangulated using dual imaging or markers that emit a signal that can be used to detect position electronically all placed prior to simulation and planning. Also, it would be acceptable to perform computed tomography such as axial, spiral or conebeam CT prior to each treatment in the treatment position to

identify the tumor target directly. Image quality should be good enough to identify the prostate borders.

In addition to the identification of the prostate in the preceding paragraph, the rectum should also be identified and reliably repositioned with a large (e.g., around 60 cc) rectal tube. Prior to positioning at least 30 minutes and no more than 2 hours before each treatment, patients should undergo an effective bowel evacuation. Typically, this will involve 1-2 fleet's enemas. This maneuver is to clear the rectum of stool and significant gas accumulation. Just prior to relocalization and treatment, a rectal tube filled with air should be introduced into the rectum to both visualize the rectum and separate the anterior and posterior walls. The rectal balloon and implementation plan must be approved by the PI prior to use.

Isocenter port localization films (anterior/posterior and lateral) should be obtained at each treatment on the treatment unit (or patients should undergo a tomographic imaging study utilizing the linear accelerator couch, if available) immediately before treatment to ensure proper alignment of the geometric center (i.e., isocenter) of the simulated fields. Verification CT scans and portal films may be taken at the discretion of the participating institution, but are not required for protocol participation.

6.4 Treatment Planning/Target Volumes

6.4.1 Image Acquisition

Computed Tomography (CT) will be the primary image platform for targeting and treatment planning. The planning CT scans must allow simultaneous view of the patient anatomy and fiducial system for stereotactic targeting. Treatment planning images should be performed in the treatment position using all aids/maneuvers described above including urethral tube, bladder contrast, urethrogram, and rectal balloon after bowel evacuation with enemas. The treatment planning scans must use a small caliber radio-opaque urethral catheter to allow visualization of the prostatic urethra as it will be a high dose spillage avoidance structure for treatment planning as indicated in section 6.4.2 below. Axial acquisitions with gantry 0 degrees will be required with spacing ≤ 3.0 mm between scans. Images will be transferred to the treatment planning computers via direct lines, disc, or tape.

Image fusion with other imaging modalities such as MRI that might be useful in delineating the target and normal tissues is encouraged.

The entire prostate without the seminal vesicles will constitute the CTV target for this protocol. It is not required to identify a GTV within the prostate, but if institutions have special techniques to identify the gross tumor, such as MRI with high tesla strength, it is encouraged to collect the contours. CTV target volume (entire prostate gland) will be outlined by an appropriately trained physician. The target will generally be drawn using CT soft tissue windows. An additional 0.3-0.5 cm in the axial plane and 0.5-1.0 cm in the longitudinal plane (cranio-caudal) will be added to the GTV to constitute the planning treatment volume (PTV) depending on the institution's accuracy and treating physician's preference.

6.4.2 Dosimetry

Three-dimensional coplanar or non-coplanar 3-D beam, arc rotation, or Intensity Modulated Radiotherapy (IMRT) beam arrangements will be custom designed for each case to deliver highly conformal prescription dose distributions. Non-

opposing, non-coplanar beams are preferable. Typically, 10-15 beams of radiation will be used with roughly equal weighting. Generally, more beams are used for larger lesion sizes. When static beams are used, a minimum of 10 non-opposing beams should be used. For arc rotation techniques, a minimum of 300 degrees (cumulative for all beams) should be utilized. For this protocol, the isocenter is defined as the common point of gantry and couch rotation for the treatment unit. Field aperture size and shape should correspond nearly identically to the projection of the PTV along a beam's eye view (i.e. no additional "margin" for dose build up at the edges of the blocks or MLC jaws beyond the PTV). As such, prescription lines covering the PTV will typically be the 60-90% line (rather than 95-100%); however, higher isodoses (hotspots) must be manipulated to occur within the target and not in adjacent normal tissue. The isocenter in stereotactic coordinates will be determined from system fiducials (or directly from the tumor) and translated to the treatment record.

The treatment dose plan will be made up of multiple static beams or arcs as described above. The plan should be normalized to a defined point corresponding closely to the center of mass of the PTV (COM_{PTV}). Typically, this point will be the isocenter of the beam rotation; however, it is not a protocol requirement for this point to be the isocenter. Regardless, the point identified as COM_{PTV} must have defined stereotactic coordinates and receive 100% of the normalized dose. Because the beam apertures coincide nearly directly with the edge of the PTV (little or no added margin), the external border of the PTV will be covered by a lower isodose surface than usually used in conventional radiotherapy planning, typically around 80% but ranging from 60-90%. The prescription dose in five fractions will be delivered to the margin of the PTV and fulfill the requirements below. As such, a "hot spot" will exist within the PTV centrally at the COM_{PTV} with a magnitude of the prescription dose times the reciprocal of the chosen prescription isodose line (i.e., 60-90%).

For purposes of dose planning and calculation of monitor units for actual treatment, all tissues within the body should be modeled in the planning system as to their electron density. Proper heterogeneity correction algorithms should be approved by the PI.

Successful treatment planning will require accomplishment of all of the following criteria:

- 1) Normalization
The treatment plan should be normalized such that 100% corresponds to the center of mass of the PTV (COM_{PTV}). This point will typically also correspond (but is not required to correspond) to the isocenter of the treatment beams.
- 2) Prescription Isodose Surface Coverage
The prescription isodose surface will be chosen such that 95% of the target volume (PTV) is conformally covered by the prescription isodose surface and 99% of the target volume (PTV) receives a minimum of 90% of the prescription dose.
- 3) Target Dose Heterogeneity
The prescription isodose surface selected in number 2 (above) must be \geq 60% of the dose at the center of mass of the PTV (COM_{PTV}) and \leq 90% of the dose at the center of mass of the PTV (COM_{PTV}). The COM_{PTV} corresponds to the normalization point (100%) of the plan as noted in 1) above.

4) High Dose Spillage

a) Location

Any dose greater than 105% of the prescription dose should occur primarily within the PTV itself and not within the normal tissues outside of the PTV. Therefore, the cumulative volume of all tissue outside of the PTV receiving a dose greater than 105% of prescription dose should be no more than 15% of the PTV volume. *However, if possible, attempts should be made to avoid higher than the prescription isodose to the prostatic urethra within the prostate.* Ideally, these hot spots will be manipulated to occur within the peripheral zones of the prostate. IMRT and other techniques will be encouraged to accomplish this goal.

b) Volume

Conformality of PTV coverage will be judged such that the ratio of the volume of the prescription isodose meeting criteria 1) through 4) to the volume of the PTV is ideally less than 1.3.

- 5) Respect all critical organ dose-volume limits listed in Section 6.5.1 below.
- 6) Urethral “hot spot” avoidance. It is recommended that efforts be made by the use of compensation or intensity modulation to avoid excessive dose to the urethra. The prostatic urethra should be identified as an avoidance structure such that dose beyond the prescription dose ideally does not fall on this structure. As an example, if the treatment dose covering the PTV corresponds to the 80% isodose line for a given patient, hot spots of 20% higher dose will exist within the prostate. The intensity modulation techniques should be employed to distribute these hot spots away from the prostatic urethra and more into the peripheral zones of the prostate. Part of the rationale for daily image guidance on this protocol is to carry out this intention of avoiding a “hot spot” to the urethra in practice during treatment as depicted on the treatment plan.

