Stereotactic body radiation therapy (SBRT) is a new therapeutic paradigm for treating localized tumors outside of the central nervous system and involves delivering very high doses of focused radiation using unique beam arrangements and special immobilization equipment [19]. As already demonstrated in lung and liver cancers, these treatments offer hope for improved local control of cancers that may translate into gains in survival especially for smaller early stage lesions. SBRT employs daily treatment doses dramatically higher than typical for conventionally fractionated radiation therapy (CFRT). In turn, it is incorrect to assume that SBRT radiobiology is similar to historical CFRT. Indeed, a unique biology of radiation response for very large dose per fraction treatments is being appreciated both in terms of tumor control as well as normal tissue consequences translating into unique clinical outcomes. For example, local control with CFRT in early stage lung cancer is consistently reported below 50% while several series using SBRT show local control around 90% [20-21].

SBRT has been defined by the American College of Radiology (ACR) and American Society of Therapeutic Radiology and Oncology (ASTRO) to involve the use of very large dose per fraction [22]. Indeed, dose per fraction of 8 Gy minimum would obviously make SBRT very different from even the more abbreviated hypofractionation schemes described above. Typically, only 1-5 fractions are used for SBRT depending on the tolerance of adjacent or intervening normal tissues. Linear structures (like the spinal cord) and tubular structures (like the bowels) are commonly called “serially functioning tissues” akin to series electrical circuits because their function is disrupted if there is a defect anywhere along their pathways [23-24]. It has been shown that serial functioning tissues are less tolerant to SBRT than so-called “parallel functioning tissues” like the peripheral lung and liver. In response, typically more fractions are employed (e.g., five fractions rather than one) when serially functioning tissue cannot be avoided. In the case of treating prostate cancer, the rectum is an adjacent serially functioning tissue while the urethra is an intervening serially functioning tissue traversing the very center of the prostate target.

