6.5 Critical Structures

6.5.1 Critical Organ Dose-Volume Limits

The following table lists maximum dose limits to a point or volume within several critical organs. These are absolute limits, and treatment delivery that exceeds these limits will constitute a major protocol violation (See Section 5.7). The dose is listed as total over 5 fractions and per fraction.

These limits were formulated with the approval of the study committee using known tolerance data, radiobiological conversion models, norms used in current practice at academic centers. Participating centers are encouraged to observe prudent treatment planning principles in avoiding unnecessary radiation exposure to critical normal structures irrespective of these limits.

In order to verify each of these limits, the organs must be contoured such that appropriate dose volume histograms can be generated. Instruction for the contouring of these organs will follow below.

Organ	Volume	Dose (cGy)
Spinal Cord	Maximum point dose	22 Gy (4.4 Gy per fraction)
	Less than 8 cc	20 Gy (4 Gy per fraction)

Cauda Equina	Maximum point dose	27.5 Gy (5.5 Gy per fraction)
	Less than 10 cc	25 Gy (5 Gy per fraction)
Sacral Plexus	Maximum point dose	30 Gy (6 Gy per fraction)
	Less than 10 cc	27.5 Gy (5.5 Gy per fraction)
Peri-prostatic Anterior rectal wall	Maximum point dose	No more than 105% of the prescription dose
Peri-prostatic Lateral rectal walls	Maximum point dose	No more than 100% of the prescription dose
	Less than 3 cc cumulative (both sides)	No more than 90% of the prescription dose
Peri-prostatic Posterior rectal wall and anus	Maximum point dose	No more than 45% of the prescription dose
Rectum superior to prostate	Maximum point dose	30 Gy (6 Gy per fraction)
	Less than 10 cc	25 Gy (5 Gy per fraction)
Small intestine	Maximum point dose	29 Gy (5.8 Gy per fraction)
	Less than 10 cc	19.5 Gy (3.9 Gy per fraction)
Prostatic urethra	Maximum point dose	No more than 105% of prescription dose
Bladder	Maximum point dose	No more than 105% of prescription dose
	Less than 10 cc	18.3 Gy (3.65 Gy per fraction)
Penile bulb	Maximum point dose	No more than 100% of prescription dose
	Less than 3 cc	30 Gy (6 Gy per fraction)
Femoral heads	Less than 10 cc cumulative (both sides)	30 Gy (6 Gy per fraction)
Skin within fold (e.g., the gluteal fold)	Maximum point dose	20 Gy (4 Gy per fraction)
Skin not within fold	Maximum point dose	27.3 Gy (5.45 Gy per fraction)

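### Where the contoured urethra contains the PTV centre of mass, the planning criteria cannot all be met: that point must receive at least 111% of prescription, but the urethral limit is 105%

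*Combined protocol and SAP*

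**What the plan says.** Section 6.4.2 introduces its planning list with "Successful treatment planning will require accomplishment of all of the following criteria". Three items on that list matter here.

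- Criterion 1: "The treatment plan should be normalized such that 100% corresponds to the center of mass of the PTV".
- Criterion 3: the prescription isodose must be at least "60% of the dose at the center of mass of the PTV" and at most "90% of the dose at the center of mass of the PTV".
- Criterion 5: the organ limits of Section 6.5.1 must be respected.

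The narrative before the list says that a central hot spot will exist at the PTV centre of mass, "with a magnitude of the prescription dose times the reciprocal of the chosen prescription isodose line".

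Section 6.5.1 describes its limits as absolute and treats any excess as a major violation. For the maximum point dose to the prostatic urethra the entry is "No more than 105% of prescription dose". Section 6.5.2.7 contours the urethra as the catheter plus 1-2 mm of tissue. Section 6.7.2 grades an excess over the organ limits differently: minor above 2.5%, major above 5%.

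On anatomy, Section 1.2 says that "the urethra is an intervening serially functioning tissue traversing the very center of the prostate target". Section 1.3 is softer and places it toward the centre.

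**The concern.** Two rules on the same mandatory list act on places that the protocol itself describes as close together or the same. One requires the centre of the PTV to be hotter than the prescription by a set minimum. The other limits how hot the urethra may be, and the limit is lower than that minimum. If the urethra runs through the centre, a planner cannot satisfy both.

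The urethra is not a minor structure here. Section 1.3 names urethral dysfunction as a likely dose-limiting toxicity. Treatment-related genitourinary toxicity of grade 3-5 is a DLT (13.1.1), and late grade 3-5 genitourinary toxicity is part of the phase II primary endpoint (13.2.1). The urethral dose rule therefore bears directly on both the escalation decision and the main result, and it should be one that a site can follow.

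**Working it through.** **Inputs.** Isodose range 60-90% of the centre-of-mass dose (6.4.2, criterion 3). Central dose = prescription × 1/(isodose fraction) (6.4.2, narrative). Urethral limit 105% of prescription (6.5.1). Dose levels 45, 47.5 and 50 Gy (schema). Violation thresholds 2.5% and 5% (6.7.2).

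**The plan's own figure.** The only worked central-dose example is in item 6 of 6.4.2: with the 80% line covering the PTV, hot spots are put at 20% higher. The protocol's reciprocal rule gives 100/0.80 = 125% of prescription, which is 25% higher. The figure of 20 is recovered only as 100 − 80, in points of the normalised dose, a different scale from the urethral limit. Both readings are above 105%, so this slip does not affect what follows.

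**Central dose under criterion 3.**

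- Minimum: 100/0.90 = 111.1% of prescription.
- Maximum: 100/0.60 = 166.7%.
- Isodose needed for a central dose of 105% or less: 100/1.05 = 95.2% or higher, which is outside the required 60-90%.

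**By dose level.**

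| Prescription | Centre, minimum (÷ 0.90) | Urethral limit (× 1.05) | Gap |
|---|---|---|---|
| 45 Gy | 50.0 Gy | 47.25 Gy | 2.75 Gy |
| 47.5 Gy | 52.78 Gy | 49.88 Gy | 2.90 Gy |
| 50 Gy | 55.56 Gy | 52.5 Gy | 3.06 Gy |

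For scale, each gap is larger than the 2.5 Gy step in total dose between cohorts. At the 80% line, which 6.4.2 calls typical, the centre receives 45/0.80 = 56.25 Gy at the lowest level and 50/0.80 = 62.5 Gy at the highest.

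**Where the two rules meet.** Criterion 3 fixes the dose at one point; 6.5.1 limits every point of a narrow structure. They exclude each other when the structure contains the point. Intensity modulation cannot help there, because a plan that lowers the centre to 105% fails criterion 3. When the urethra lies off that point, a modulated plan might meet both.

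**Violation thresholds, urethra at the 50 Gy level.** The limit is 52.5 Gy; 2.5% over is 52.5 × 1.025 = 53.81 Gy; 5% over is 52.5 × 1.05 = 55.13 Gy. Above 52.5 and up to 53.81 Gy, an excess is major under 6.5.1 and no violation under 6.7.2. Above 53.81 and up to 55.13 Gy it is major under 6.5.1 and minor under 6.7.2. This disagreement holds wherever the urethra lies.

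**The case against.** The strongest reply is geometric. The statement in 1.2 is background on serial tissues, not a planning definition, and 1.3 says only that the urethra lies toward the centre. The rule concerns the centre of mass of the PTV, which adds margins around the prostate, and the narrative in 6.4.2 asks only that the normalisation point correspond closely to it. No document gives the distance from urethra to centre. This stands. A reader might infer that sites must break one rule or the other in every patient; the documents do not support that.

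A reader might also see a contradiction between the absolute limit and the softer text in 6.4.2, for example "It is recommended that efforts be made by the use of compensation or intensity modulation to avoid excessive dose to the urethra". They can be read together. The soft wording concerns excessive dose, or dose above 100% of prescription, while the absolute limit is 105%. A goal of 100% with a hard limit of 105% is a coherent two-tier rule.

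A third inference is that the tolerance in 6.7.2 cannot close the gap. On the urethral side alone, 105% × 1.05 = 110.25%, still below 111.1%. But a central dose of 110.25% corresponds to an isodose of 100/1.1025 = 90.7%, so an allowance of less than one point on criterion 3 would bring the plan to the edge of the major threshold in 6.7.2. Section 6.7.2 refers to a deviation table in Section 6.4 that is not in the text available and may have been lost in extraction. The claim therefore holds only if criterion 3 has no allowance.

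Finally, one might infer that urethral dose and violation counts will differ by site. Nothing in the documents shows this. Dose construction at each site is approved beforehand (5.3.1), and radiotherapy quality assurance is reviewed every 20 cases (6.8). Those safeguards do not cure the wording, but they weigh against assuming the consequence.

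**Conclusion.** The point holds in a conditional form. If the contoured urethra contains the normalisation point, criteria 3 and 5 of Section 6.4.2 cannot both be strictly met. The required minimum is 111.1% against a limit of 105%, a difference of 6.1 points of prescription, or 2.75 to 3.06 Gy across the dose levels. This rests on the protocol's own reciprocal rule and on reading criterion 3 without tolerance. How many patients are affected cannot be told from the documents. The clash between 6.5.1 and 6.7.2 over what counts as a major violation needs no anatomical assumption.

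**What to change.** Reconcile the normalisation and heterogeneity criteria in 6.4.2 with the urethral limit in 6.5.1, so that both can be met when the urethra runs through the centre of the PTV. Reconcile the violation thresholds in 6.5.1 and 6.7.2, so that an excess over an organ limit has one classification. Which limit or criterion changes, and to what, is for the study committee. The cost is protocol wording, with no extra patients or procedures.
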